In the open-label study, participants' Children's Depression Rating Scale (CDRS-R) scores were reduced by 44% [55]. Moreover, utilizing pre- and post-treatment brain scans we found that brain PCr concentrations increased with eight weeks of creatine supplementation when compared to a comparison group of non-depressed adolescent controls [55]. In the dose-ranging study, participants were randomly assigned to treatment from one of the four study drug groups for 8 weeks. Participants randomized to all creatine treatment groups showed greater decreases in CDRS-R scores, with reductions between 28-42%, compared to the CDRS-R scores of participants randomized to placebo, who showed a decrease of 24% [unpublished data]. Participants treated with 10g daily creatine showed the highest increases in frontal lobe PCr, and were the only participants showing post-treatment increases in frontal lobe beta-NTP. In both studies, creatine was well-tolerated, and participants experienced no suicide attempts or psychiatric hospitalizations over the 8-week trial. We observed no persistent or clinically significant abnormalities on serum or urine laboratory tests.

The neuroimaging and clinical results from the R21 study suggest that daily adjunctive treatment of 10g creatine is associated with the greatest change in PCr, and higher PCr is associated with lower depression scores. Therefore, the dose of creatine our data suggests is most likely to engage the neurochemical target is the 10g dose. At the same time, our data do not suggest that the 10g dose poses significantly greater risks to subjects compared with placebo, other than weight gain attributable to intracellular water.

The current protocol seeks to expand upon our previous work by opening recruitment on a pilot study of creatine 10g daily vs. placebo as a treatment for female adolescents with SSRI-resistant MDD. The purpose of the pilot study is twofold: A) to evaluate several aspects of the feasibility of creatine supplementation as a treatment for this population; and B) to estimate the

effect size of adjunctive creatine, to inform the design and implementation of a potential future efficacy trial.

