use in child psychiatry is novel. Creatine's gender-specific effects in animal models mandate that studies in youth be initially limited to female participants. Expanding upon our group's recent completion of a multidose study to establish which of four daily creatine doses offers the best combination of efficacy, safety and tolerability in adolescent females with SSRI-resistant MDD, we propose to conduct a pilot, placebo-controlled study of 10g daily adjunctive creatine, the dose selected from the dose-ranging trial, for adolescent females with SSRI-resistant MDD. We propose to examine the relationship between depression severity and cerebral PCr and to measure the effect size of adjunctive creatine vs. placebo on brain chemistry and clinical outcome in adolescent females with SSRI-resistant MDD.

OBJECTIVES:

The primary hypothesis is that compared to placebo, 10g of daily creatine monohydrate for eight weeks will be associated with significant increases in frontal lobe PCr and β -NTP concentrations. A secondary hypothesis is that decreased depressive symptoms measured with the CDRS-R and Montgomery Asberg Depression Rating Scale (MADRS) will be reciprocally correlated with increased β -NTP concentrations.

PARTICIPANT SELECTION CRITERIA:

Thirty-three female adolescents with MDD will be randomly assigned in a 1:1 ratio to either treatment for eight weeks, for a total of 66 MDD participants. Additionally, 40 healthy adolescents will be recruited as comparison subjects for the study. Key inclusion, exclusion, and study withdrawal criteria for each subject group are summarized below.

MDD SUBJECTS

Inclusion Criteria:

- Participants must be female.
- Participants must be able to grant informed consent (age ≥ 18), or parent/guardian permission plus participant assent (age < 18).
- Participants must meet DSM-IV criteria for MDD, with current mood state depressed for > 2 weeks.
- Participants must be between the ages of 12 and 21.
- Current CDRS-R raw score of ≥ 40 or MADRS score ≥ 25 ; and CGI-S score ≥ 4 .
- Participants may be enrolled in individual and/or group psychotherapy, if it has been ongoing for at least 8 weeks.

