- Participants must have been in treatment with an SSRI for at least 8 weeks, the last 4 of which were at a dosage of ≥ 20 mg per day of fluoxetine or its equivalent, e.g. 20 mg per day of paroxetine, 20 mg citalopram, 10 mg escitalopram, or 100 mg sertraline. If the participant attempted, but could not tolerate, a dose comparable to 20 mg fluoxetine, they will be considered eligible. (This definition of "Adolescent SSRI Resistant Depression" is modified from the NIH-sponsored, \$17 million TORDIA Randomized Controlled Trial [<http://clinicaltrials.gov/ct2/show/NCT00018902>] [128].

Exclusion Criteria:

- Unstable co-morbid medical, neurological, or psychiatric disorder.
- Current DSM-IV criteria for substance abuse or dependence (excepting nicotine/cigarettes).
- Clinically significant suicidal or homicidal risk.
- Pre-existing renal disease.

- Proteinuria on baseline urinalysis testing.
- Pregnancy or breastfeeding.
- Sexually active and unwilling to practice contraception during the study.
- Contraindication to magnetic resonance imaging (e.g. ferromagnetic implant or claustrophobia)
- History of hypersensitivity to creatine.
- History of a previous failed therapeutic trial of creatine.
- Participants may be outpatients or inpatients, but incarcerated persons will be excluded because this study is not approved for "Research Involving Prisoners."
- More than 2 suicide attempts prior to the screening visit
- Participants who made a suicide attempt within 6 months prior to the screening visit

Study Withdrawal Criteria:

- Withdrawal of parental permission, participant informed consent, or participant assent.
- Onset of a psychotic disorder or bipolar disorder.
- Intolerable or clinically significant side effects to creatine.
- Worsening depression, as demonstrated by an increase in CDRS-R or MADRS score $>25\%$ from baseline.
- Positive pregnancy test.
- A significant change to the participant's medication or psychotherapy treatment from the regimen reported at their baseline/screening visit (e.g. the SSRI is discontinued).
- Incarceration, as the study is not approved to conduct "Research Involving Prisoners."
- If a clinically significant intracranial lesion is found by the Radiologist on a participant's baseline brain scan, they will be withdrawn from the study and referred for appropriate medical care.

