- It is possible that the participant's illness could worsen during the study. This could be related or unrelated to the study. Adolescents with Major Depressive Disorder are at risk for depression, suicidal ideation, and suicide attempts as part of their illness. Physicians working on the study will be available 24 hours per day. If the participant's illness worsens to the point that the study doctor considers them a danger to themselves or others, they will be hospitalized. If the participant is hospitalized they will be withdrawn from the study. In the event of hospitalization, the participant or the participant's insurance company will be responsible for the associated costs.
- It is possible that treatment with creatine will not be effective for the participant's depression, and that study participation will therefore delay the start of effective treatment.
- The researchers will take precautions to safeguard the participant's confidentiality, but it is possible that a breach of confidentiality could occur. A Certificate of Confidentiality has been obtained for this study.
- The participants may experience gastrointestinal discomfort as a result of taking study medication. We recommend taking the study medication with food to reduce possible stomach discomfort.
- MRI/MRS scans do not use ionizing radiation like x-rays or CT scans. Instead, magnetic fields and radio waves are used to take the pictures. There are no known risks related to MRI scans – other than the risk of injury when metallic objects are brought into the scanning room by mistake. Serious injury can occur during an MRI scan to persons who have:
 - Cardiac (heart) pacemakers.
 - Metal clips on blood vessels (also called stents).

- Artificial heart valves.
- Artificial arms, hands, legs, etc.
- Brain stimulator devices.
- Implanted drug pumps.
- Cochlear (ear) implants.
- Ocular (eye) implants or known metal fragments in eyes.
- Exposure to shrapnel or metal fillings
- Other metallic surgical parts.
- Orthodontic braces on the teeth.
- Body jewelry or piercings that cannot be removed for the scan.
- Certain tattoos with metallic ink (please tell us if your child has a tattoo)
- Certain transdermal (skin) patches such as NicoDerm (nicotine for tobacco dependence),
- Transderm Scop (scopolamine for motion sickness), or Ortho Evra (birth control)

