We hypothesize that at baseline, CDRS-R scores are negatively correlated with cerebral PCr in female adolescents with SSRI-resistant MDD. We also hypothesize that for participants whose MDD responds to creatine, change CDRS-R score will be inversely correlated with change in brain beta-NTP levels (i.e. participants who have a significant decrease in their CDRS-R score will show an increase in beta-NTP).

Both intent-to-treat (ITT; encompasses all participants who receive >1 dose of study drug) and protocol completer analyses will be performed. A participant completing 8 weeks of treatment and both ^{31}P -MRS scans will be considered a "completer." Data will be expressed as mean + standard deviation (SD). Group differences in demographic variables involving continuous data will be calculated using one-way analysis of variance. Between-group comparisons involving categorical variables will be assessed using Fisher's exact test for n x k contingency tables. A linear mixed model (LMM) will be used to account for the association between measurements (baseline and post-treatment) for each individual for the repeated measures analysis. Exploratory data analysis using non-parametric statistical tests (e.g., Wilcoxon Rank-Sum test and the Mann-Whitney U-test) will also be performed. Statistical significance will be defined at the two-tailed, 0.05 level. Stata 11 (StataCorp LP, College Station, TX) and SAS 9.2 (SAS Institute, Cary, NC) software will be used for statistical calculations. Confidence intervals for all estimated parameters will be constructed using a 95% level.

Power Analysis and Sample Size Calculations: Calculations are based on the open-label female adolescent SSRI-resistant MDD creatine data obtained at our site, and our adult creatine studies. All power calculations are two-tailed with an alpha level of 0.05, and were performed in the specialized software PASS (NCSS, Kaysville, UT). The minimum required sample size

satisfying our hypothesis is 30 creatine-treated, 30 placebo-treated, and 30 age-matched healthy controls. Assuming a 10% attrition rate for MDD subjects and a 30% attrition rate for healthy controls, we propose to enroll a total of 66 female adolescents with SSRI-resistant MDD and 40 healthy controls. The central hypothesis and power analysis for the R33 clinical trial are described below.

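### No CDRS-R or MADRS analysis is defined after withdrawal for worsening; a baseline-to-Week-8 mixed model can bias the arm difference, in a direction the documents do not fix

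*Combined protocol and SAP*

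**What the plan says.** Four parts of the combined protocol and SAP bear on this.

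- **Withdrawal.** The Study Withdrawal Criteria for MDD subjects include "Worsening depression, as demonstrated by an increase in CDRS-R or MADRS score" of more than 25% from baseline. Risks and Benefits to Study Participants adds a second route: "If the participant is hospitalized they will be withdrawn from the study".
- **Aim.** The last background paragraph before Objectives proposes "to measure the effect size of adjunctive creatine vs. placebo on brain chemistry and clinical outcome". The purpose of the pilot includes estimating the "effect size of adjunctive creatine, to inform the design and implementation of a potential future efficacy trial".
- **Analysis.** Statistical Analyses states: "A linear mixed model (LMM) will be used to account for the association between measurements (baseline and post-treatment) for each individual". On analysis sets it says: "Both intent-to-treat (ITT; encompasses all participants who receive >1 dose of study drug) and protocol completer analyses will be performed". It gives no rule for missing or post-withdrawal scores. The data management section gives only a database code for missing values.
- **Schedule.** Table 1 places the depression scales at several visits between baseline and Week 8. The Neuroimaging Protocol has two scans only, at baseline and after 8 weeks.

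**The concern.** A participant who worsens enough leaves the study, and her Week 8 rating is then missing because of how she was doing. The ratings that record the worsening have been collected, but a model with only baseline and Week 8 does not use them. The ITT set gives little protection: a withdrawn participant adds her baseline value and nothing else, so the ITT result stays close to the completer result.

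At stake is the clinical effect estimate that the pilot is meant to pass on to a later efficacy trial. The placebo improvement is affected too, because the participants who got worse drop out of the Week 8 mean.

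**Working it through.** **1. Two readings of post-treatment.** If it means Week 8, the triggering rating is excluded. If it means the last rating obtained, that rating is included. The plan does not say which applies, nor that the model sentence covers CDRS-R and MADRS at all.

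**2. What the two-point model estimates.** By maximum likelihood, the Week 8 mean in an arm is

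mean(Week 8, completers) + b × [mean(baseline, all) − mean(baseline, completers)],

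with b the pooled slope of Week 8 on baseline. This is unbiased only if withdrawal tells us nothing about Week 8 once baseline is known. Here withdrawal is decided by the interim ratings, which predict Week 8, so the condition fails.

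**3. Inputs.** The plan states no SD, power or effect size for the clinical scales, so there is no figure of its own to reproduce.

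- From the documents: CDRS-R declines of 24% (placebo) and 28-42% (creatine doses; the 10 g figure is not given separately); entry thresholds of 40 (CDRS-R) and 25 (MADRS); the 25% rule on either scale; 33 per arm.
- Assumed: CDRS-R baseline mean 55, SD 8; MADRS baseline mean 31, SD 5; correlation 0.5; linear percent change with correlation 0.8 between scales; visit error SD 6 and 3.4; score floors 17 and 0; ratings at Weeks 0, 1, 2, 3, 4, 6 and 8 (Table 1 is broken in the extract); SD of percent change 15%, 25% or 30%.

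**4. Equal spread in both arms, 42% versus 24%.** The difference is the extra CDRS-R points of improvement on creatine.

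| SD of % change | Withdrawn overall | True difference | Two-point | Kept | All-visit model keeps | Last rating keeps |
|---|---|---|---|---|---|---|
| 15% | 2.6% | 9.80 | 9.61 | 98% | 99.7% | 102% |
| 25% | 5.9% | 9.18 | 8.05 | 88% | 97% | 100% |
| 30% | 8.6% | 8.60 | 6.86 | 80% | 95% | 98% |

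The loss is therefore about 2%, 12% and 20%. Withdrawals stay inside the plan's own allowance ("Assuming a 10% attrition rate for MDD subjects and a 30% attrition rate for healthy controls"). With CDRS-R as the only trigger, the losses are 1%, 8% and 14%. Placebo improvement is overstated by 0.3, 1.7 and 2.9 points with both triggers.

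**5. Unequal spread.** Positive values favour creatine.

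| Decline, creatine vs placebo | SD, creatine vs placebo | True | Two-point | All-visit |
|---|---|---|---|---|
| 28% vs 24% | 30% vs 20% | 1.49 | 3.11 | 2.06 |
| 24% vs 24% | 25% vs 20% | −0.22 | 0.68 | 0.07 |

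In the first row the two-point error is 3.11 − 1.49 = 1.62 points in favour of creatine. The all-visit error is 2.06 − 1.49 = 0.57, so about two-thirds is removed (1.05/1.62 = 65%). In the second row the errors are 0.90 and 0.29.

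**6. Size at 33 per arm.** Equal spread, 42% versus 24%, both triggers; SE = √(RMSE² − bias²).

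| SD | Two-point bias | Two-point RMSE | SE | Bias/SE | All-visit bias | All-visit RMSE |
|---|---|---|---|---|---|---|
| 15% | −0.24 | 2.60 | 2.59 | 0.09 | −0.06 | 2.62 |
| 25% | −1.08 | 3.63 | 3.47 | 0.31 | −0.20 | 3.56 |
| 32% | −2.00 | 4.49 | 4.02 | 0.50 | −0.50 | 4.22 |

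For the first row of step 5, setting 1.62 against the SE of 3.47 from the SD 25% case gives 0.47, a rough comparison of the same order.

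**The case against.** The strongest reply is that the problem needs several conditions. The model sentence must apply to the clinical scales, post-treatment must mean Week 8, and responses must vary widely. If the last rating counts as post-treatment, the bias is small. The stated hypotheses about CDRS-R are correlations, and the arm difference is an aim of estimation, not a test. At 28% versus 24% with equal spread, the loss is only a fraction of a point and the all-visit model has slightly larger total error (RMSE 4.25 against 4.06 at SD 32%, or 4.7% more). All of this stands. It limits the size of the point but does not supply the missing definition.

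A reader might infer that the clinical estimate is at least conservative, with error running only toward no effect. The documents do not support that. They give no SD by arm, and step 5 shows the sign reversing when creatine responses are more variable, even with equal means.

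A reader might also infer that the primary metabolite outcome is untouched because it is scanned only twice. That does not follow. Someone withdrawn early has no scheduled Week 8 scan, and the plan itself expects CDRS-R change to track beta-NTP change.

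Hospitalisation is a further route, but of the two earlier studies the background reports that "participants experienced no suicide attempts or psychiatric hospitalizations over the 8-week trial", so it is not in the figures.

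**Conclusion.** The gap is real and worth correcting, though modest. Missingness is tied to the clinical outcome, and neither the model's outcome nor its post-treatment value is defined for withdrawn participants. Under the Week 8 reading, the arm difference can be biased. About 2-20% is lost if creatine is better, spread is similar, the decline is 42% versus 24% and the SD is 15-30%. The bias can instead favour creatine if that arm is more variable. It reaches at most about half a standard error at 33 per arm in the cases examined. Every size here depends on assumed SDs, and the 42% figure is the most favourable of the earlier creatine results. Nothing here suggests that the trial is invalid. The argument for change is lower bias from ratings already scheduled, not better precision.

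**What to change.** State the CDRS-R and MADRS analysis and define post-treatment for withdrawn participants.

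- Fit the mixed model to all scheduled double-blind ratings from baseline to Week 8, including the rating at withdrawal. Use arm, visit and arm-by-visit terms and an unstructured covariance, with a simpler structure named in advance in case it does not converge.
- Report the Week 8 arm difference with its 95% confidence interval.
- Report by arm the number withdrawn for worsening or hospitalisation.
- Add one sensitivity analysis: a joint model of both scales, or the last rating used as post-treatment. The latter is a different quantity, status at the end of participation.

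Because either scale can trigger withdrawal, and because spread may differ by arm, a single-scale model reduces the bias without fully removing it. The change cannot help PCr and beta-NTP, which have no interim scans. Report instead that their Week 8 values are missing for the same withdrawn participants. The withdrawal rule stays unchanged.

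The cost is SAP wording and somewhat more modelling, with no new data. Seven visits need 7 × 8 / 2 = 28 covariance parameters with 66 participants, hence the fallback. Total error may be slightly larger, up to about 5% in these runs, if the true effect is small.

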- The principal investigator retains the right to withdraw participants from the study without their permission, in the event they are unwilling or unable to maintain adherence to the research protocol.

HEALTHY COMPARISON SUBJECTS

Inclusion Criteria:

- Participants must be able to grant informed consent (age >18), or parent/guardian permission plus participant assent (age <18).
- Participants must be female.
- Participants must be between the ages of 12 and 21 years.
- Participants must not meet DSM-IV-TR criteria for a current psychiatric illness or substance use disorder.
- Participants must have a CDRS-R score ≤ 30 .

Exclusion Criteria:

- Unstable medical or neurological illness.
- Clinically significant psychiatric or substance use disorder.
- Pregnant subjects, due to the unknown effects of MRI/MRS scans on a fetus. In addition, women of childbearing potential who are unable or unwilling to practice contraception during the study will be excluded. Female participants who are of childbearing potential must have a negative urine pregnancy test before the MRI/MRS scan.
- Participants with a contraindication to MRI/MRS scanning, such as a metallic implant.

Study Withdrawal Criteria:

- Withdrawal of parental permission or participant assent.
- Onset of a psychotic disorder or depression.
- Positive pregnancy test.
- A significant change to the participant's medication or psychotherapy treatment from the regimen reported at their baseline/screening visit, unless directed by the principal investigator.

DESIGN:

The proposed study will use a randomized double-blind placebo-controlled design. Sixty-six participants will be randomly assigned in a 1:1 ratio to placebo or 10g of oral daily creatine monohydrate augmentation for eight weeks.

The study's design is consistent with the acceptable ethical justifications for the use of placebo controls outlined in the University of Utah Institutional Review Board's (IRB's) Investigator Guidance on Placebo Comparators (Version B0608). Specifically, this study fits situations #3, #4 and #5 of the Guidance:

- "*Participants are refractory to the available therapies by virtue of their past treatment history*" (#3): by definition, the proposed study will recruit female adolescents with SSRI-resistant a.k.a. treatment-refractory depression. To meet the study's inclusion criteria, participants must have failed an adequate trial of the standard-of-care intervention.

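### Forty healthy controls at the assumed 30% attrition leave an expected 28, not the stated minimum of 30; the MDD target misses only by rounding

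*Combined protocol and SAP*

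**What the plan says.** The paragraph on power analysis and sample size, under Statistical Analyses, gives the minimum "satisfying our hypothesis is 30 creatine-treated, 30 placebo-treated, and 30 age-matched healthy controls". The next sentence sets two loss rates, "Assuming a 10% attrition rate for MDD subjects and a 30% attrition rate for healthy controls", and on that basis continues: "we propose to enroll a total of 66 female adolescents with SSRI-resistant MDD and 40 healthy controls".

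The same targets appear elsewhere. The Design section says "Sixty-six participants will be randomly assigned in a 1:1 ratio to placebo or 10g of oral daily creatine monohydrate", which is 33 per arm, and Participant Selection Criteria says "40 healthy adolescents will be recruited as comparison subjects for the study". The protocol gives no inflation formula, rounding rule or replacement allowance that would link the minimum to the targets.

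**The concern.** An allowance for attrition should leave the required number after the assumed losses. A reader who applies the stated rates to the stated targets gets 28 controls where the plan calls 30 the minimum. The minimum, the attrition rate and the target for controls cannot all stand as written.

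What is at stake is the internal consistency of the sample-size statement. If 30 controls really are the minimum, the plan does not expect to have them. If 28 is acceptable, 30 is not a minimum.

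**Working it through.** **Inputs, all from the sample-size paragraph and the Design section**
- Required after losses: 60 MDD (30 per arm) and 30 controls.
- Attrition: 10% for MDD, 30% for controls.
- Enrolment: 66 MDD (33 per arm) and 40 controls.

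**1. Trying to reproduce the plan's targets**

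The standard allowance is required number / (1 − attrition).
- MDD: 60/0.90 = 66.7, so 67, or 68 if each arm is rounded up (30/0.90 = 33.3, so 34). The stated 66 is within one or two participants.
- Controls: 30/0.70 = 42.9, so 43. The stated 40 is 3 short.

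A common alternative is required number × (1 + attrition), which does not preserve the required number.
- MDD: 60 × 1.10 = 66, an exact match.
- Controls: 30 × 1.30 = 39, close to 40 but not equal.

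**2. What the stated targets retain:** enrolled × (1 − attrition)
- MDD: 66 × 0.90 = 59.4; per arm, 33 × 0.90 = 29.7.
- Controls: 40 × 0.70 = 28, which is 2 of 30 (about 7%) below the minimum.

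**3. Attrition that the targets do allow for:** 1 − required/enrolled
- MDD: 1 − 60/66 = 9.1%.
- Controls: 1 − 30/40 = 25%.

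**4. Chance of reaching the minimum**

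This assumes that losses are independent and occur at exactly the stated rates (binomial).
- At least 60 of 66 MDD participants retained: 0.51.
- At least 30 of 40 controls retained: 0.31.

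The MDD target is about an even chance. The control target is more likely to be missed than met.

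**5. Effect of the MDD gap on power**

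The plan's inputs are an effect size of d = 0.9 and "All power calculations are two-tailed with an alpha level of 0.05". For a two-sample t-test with n per arm, the noncentrality is d × √(n/2).
- n = 30: 0.9 × √15 = 3.49, power 92.9%.
- n = 29.7: 0.9 × √14.85 = 3.47, power 92.6%.
- n = 29: 0.9 × √14.5 = 3.43, power 92.0%.

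The expected shortfall costs 0.3 of a percentage point.

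**6. Where the controls enter**

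The only power calculation compares metabolite changes between creatine and placebo and does not use the controls. Table 1 gives controls one scan, at week 0. None of the hypotheses under Objectives or Statistical Analyses involves them.

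**The case against.** The strongest reply is that nothing depends on this. The MDD gap is 0.6 of a participant in total, 29.7 per arm rounds to 30, and 66 is a natural even total for 1:1 allocation. The controls feed no stated hypothesis and no power calculation. The protocol describes a pilot meant to assess feasibility and estimate effect size. It also plans an intent-to-treat analysis with a mixed model, so MDD dropouts are not simply discarded, although one without a week-8 scan adds little on change. All of this stands. It limits the weight of the point and removes the MDD figure as a complaint in its own right. It does not explain why 40 is given as the number that yields 30 after 30% attrition.

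Three stronger readings are tempting, and the documents do not support them.
- **Every group falls below its minimum, so the trial is underpowered.** For MDD the gap is rounding, and power barely moves. For controls no power is claimed.
- **The investigators multiplied by (1 + attrition).** This fits 66 exactly but gives 39, not 40, for controls, and no working is shown. It is a possible cause, not an established one.
- **Power quoted at the reduced numbers would look worse than stated.** The plan states 86%. At d = 0.9 a t-test gives 92.9% with 30 per group and 92.0% with 29, so the quoted power would rise. That the 86% does not reproduce is a separate point and should not be mixed with this one.

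**Conclusion.** The point holds for the healthy controls. The plan's own figures give an expected 28 against a stated minimum of 30, and 43 would have to be enrolled to expect 30. The MDD figures, 59.4 against 60, agree to within rounding.

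The conclusion assumes that attrition applies to the enrolled number, as the paragraph's wording implies, and that there is no replacement, since none is described. It concerns expected numbers: the trial may still retain 30 or more controls, with a chance of about 0.31 under the binomial assumption. The arithmetic is certain and the consequence small. The creatine-placebo power statement is not affected by the control shortfall, and the documents give no ground for saying that recruitment must increase.

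**What to change.** Keep enrolment at 66 and 40 and change one sentence in the sample-size paragraph, in one of two ways.
- If 10% and 30% are the real expectations, state the expected evaluable numbers as about 59 MDD (29 to 30 per arm) and 28 controls, and stop calling 30 controls a minimum that the design delivers.
- If 30/30/30 is to stand, state the attrition that the targets allow for: about 9% for MDD and 25% for controls.

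The first is preferable unless there is a reason to expect lower losses. Either costs one sentence and leaves recruitment, conduct and analysis unchanged. Leave the power figure out of this edit; its failure to reproduce needs its own correction.
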